## 5. TREATMENT OF SUBJECTS

### 5.1 Investigational product

Patients will be randomly allocated to open-label GTN (5 mg/24 hours) administered as a transdermal patch by paramedics in the prehospital setting within 3 hours of stroke onset and continued for 24 hours, or to standard care alone. If patients are randomised to treatment with GTN but prove not to have a transient ischaemic attack (TIA) or stroke after examination in the hospital, the patch will be removed. This will not be registered as a protocol deviation or protocol violation. In the unlikely scenario that a patient will be transferred to a hospital that does not participate in the study, the patch will be removed as soon as possible. This will be considered a protocol violation. In case the patient will be transported by the ambulance from one to another hospital, i.e. to receive intra-arterial treatment, and has not yet been included in MR ASAP but does fulfil all eligibility criteria, the patient can be included in MR ASAP.

### 5.2 Use of co-intervention

Patients in each study group will be treated according to national and international guidelines and local protocols of ischaemic stroke, intracerebral haemorrhage, or any other condition that may be diagnosed. Participation in this study is NOT a contra-indication to e.g., intravenous thrombolysis or intra-arterial treatment for ischaemic stroke or surgical treatment for intracerebral haemorrhage. Participation in this study does also not preclude inclusion in a subsequent intervention study, as long as this is not directed at blood pressure modification (see explanatory flowchart and text in Appendix 2).

### 5.3 Escape medication and early termination of active treatment

Any reduction or increase in blood pressure that requires treatment according to the treating physician or paramedic may be treated according to local or national protocols or guidelines. If symptomatic falls in blood pressure occur, a stepped approach to management may be practiced (as done in ENOS):

- Monitor closely;
- Raise the patient's legs;
- Administer intravenous saline or colloid;
- Remove GTN patch.

Headache may also be treated according to local protocols and practice. If during the course of the first 24 hours it becomes apparent that the patient fulfils one of the exclusion criteria,

the patch will be removed. In case of discharge from the hospital within 24 hours, the patch will be removed. This will not be registered as a protocol deviation or protocol violation.

## 6. INVESTIGATIONAL PRODUCT

### 6.1 Name and description of investigational product

Glyceryl trinitrate (GTN), also known as nitroglycerin, is a vasodilator used in cardiac diseases. It exerts a spasmolytic action on smooth muscle, particularly in the vascular system. This action is more marked on the venous capacitance vessels than the arterial vessels. By direct action and through the reduction of myocardial wall tension, GTN also lowers the resistance to flow in the coronary collateral channels and allows re-distribution of blood flow to ischaemic areas of the myocardium.

For details we refer to the relevant SmPC. Note that for this off-patent drug, a wide range of SmPCs is available, with subtle differences. Annual review of the SmPC will only lead to amendments to the study protocol in case of new clinical findings that are of direct relevance to the study population.

ATC-Code: C01DA02 Organic nitrates.

#### Indication

Prophylaxis of angina pectoris alone or in combination with other anti-anginal therapy.

#### Contraindications

- Known hypersensitivity to nitrates or to the adhesives used in the patch;
- Raised intracranial pressure including that caused by head trauma or cerebral haemorrhage;
- Acute circulatory failure associated with marked hypotension (shock);
- Myocardial insufficiency due to obstruction, as in aortic or mitral stenosis or constrictive pericarditis;
- Marked anaemia;
- Closed angle glaucoma;
- Severe hypotensive conditions (systolic blood pressure less than 90 mm Hg);
- Severe hypovolaemia;
- Hypertrophic obstructive cardiomyopathy;
- Aortic stenosis and mitral stenosis;
- Constrictive pericarditis;
- Cardiac tamponade;
- Concomitant use of phosphodiesterase type-5 inhibitors. Phosphodiesterase type-5 inhibitors (e.g. sildenafil, tadalafil, vardenafil) have been shown to potentiate the

hypotensive effects of nitrates, and their co-administration with nitrates or nitric oxide donors is therefore contra-indicated;

## 6.2 Summary of findings from non-clinical studies

We refer to the SmPC, filed under D2.

## 6.3 Summary of findings from clinical studies

For findings in clinical studies of GTN in general, we refer to the SmPC, and for studies of GTN in patients with stroke we refer to chapters 1 and 13.

## 6.4 Summary of known and potential risks and benefits

We refer to the structured risk analysis in chapter 13.

## 6.5 Description and justification of route of administration and dosage

The route of administration and dosage as set out in paragraph 6.6. are based on the previous randomised trials ENOS and RIGHT of GTN in patients with acute stroke. In these trials, including a total of over 4000 patients, GTN as administered via a transdermal patch in a dose of 5 mg per day for a maximum duration of 7 days proved to be safe. GTN appeared only to be effective if started within 6 hours of stroke onset, and the potentially beneficial mode of action is therefore probably limited to the first hours. In addition, we aim at improving the collateral circulation before reperfusion in patients with ischaemic stroke, for which therapies (IVT; IAT) are started within the first six hours and have their effect during the first day. In patients with intracerebral haemorrhage, reduction of blood pressure is also likely to have largest effect during the first day. For these reasons, we have selected a maximum duration of treatment in MR ASAP of 24 hours rather than 7 days.

## 6.6 Dosages, dosage modifications and method of administration

GTN will be administered as a single patch which contains 18.7 mg GTN. The average amount of GTN absorbed from each patch in 24 hours is 5 mg. The patch will be applied to healthy, undamaged, relatively crease-free and hairless skin at the front or side of the chest, the upper arm, thigh, or shoulder. Skin care products should not be used before applying the patch. The patch will be removed after 24 ± 2 hours, or earlier if clinically indicated. If the patch will be detached inadvertently before the end of the 24-hour period, the same patch will be applied.

### 6.7 Preparation and labelling of Investigational Medicinal Product

The following information will be included on labels

- a) name and telephone number of the chief investigator;
- b) the name and strength of the product, pharmaceutical dosage form, route of administration, and quantity of dosage units;
- c) the batch number to identify the contents and packaging operation;
- d) “Uitsluitend voor in MR ASAP” (“only for MR ASAP”);
- e) the storage conditions;
- f) expiry date in month/year format and in a manner that avoids any ambiguity.

### 6.8 Drug accountability

The IMPs will be labelled and distributed to the ambulance services by the central pharmacy at UMC Utrecht. Each participating service will store the patches under prespecified, secured conditions. Each ambulance will have just two patches on board. As soon as one of these has been used, this will be replaced from the central storage. In each patient randomised to GTN, the batch number, subject identification number, and the time the patch is removed from the patient will be recorded by the investigator’s team at the admitting hospital. After removal, the patch will be destroyed according to local regulation.

## 7. NON-INVESTIGATIONAL PRODUCT

Not applicable.

## 8. METHODS

### 8.1 Study parameters/outcomes

Of the following parameters, only NIHSS at 24 hours and Barthel Index, EuroQol, home time, and patient location at 90 days are additional measurements as compared to standard care.

#### 8.1.1 Main study outcome

The primary outcome measure is the score on the modified Rankin Scale (mRS) at 90 days ( $\pm 14$  days). The mRS is the preferred disability parameter for clinical trials in stroke. The mRS is an ordinal hierarchical scale incorporating six categories from 0 up to and including 5, and describes the range of disability encountered post stroke. 'Death' is assigned a score of 6.

#### 8.1.2 Secondary study parameters/outcomes

##### On admission to the hospital:

- Vital signs: first measured systolic and diastolic blood pressure, pulse, and body temperature;
- Collateral circulation, as assessed with CTA (only in patients in whom CT angiography is performed as part of routine clinical care);
- Lesion size: volume of the perfusion deficit (only in patients in whom CT perfusion is performed as part of routine clinical care) or ICH on the initial CT;

##### At 24 hours ( $\pm 4$ hours):

- Treatment with intravenous thrombolysis;
- Intra-arterial treatment;
- Vital signs: systolic and diastolic blood pressure, pulse, and body temperature;
- Neurological deficit, as assessed with the NIHSS;

##### At 7 days ( $\pm 1$ day) or at discharge, if earlier:

- SAEs in the first 7 days or until discharge, if earlier;

##### At 90 days ( $\pm 14$ days):

- Death;
- Dichotomized mRS of 0-1 vs. 2-6;
- Dichotomized mRS of 0-2 vs. 3-6;
- Dichotomized mRS of 0-3 vs. 4-6;
- Disability assessed with the score on the Barthel Index (BI);
- Quality of life assessed with the EuroQol 5D-5L (EQ-5D-5L);

- Home time: the number of nights among the first 90 days since stroke onset that are spent in the patient's own home or a relative's home. Where final follow-up occurs earlier, the last known placement will be extrapolated to 90 days;
- Patient location over first 90 days ( $\pm$  14 days): hospital; rehabilitation service; chronic nursing facility; home.

### 8.1.3 Other study parameters

Baseline characteristics, assessed as part of routine clinical care at the time of the initial assessment by the paramedics. The last assessments before study inclusion should be reported.

- Age; sex;
- Vital signs: systolic and diastolic blood pressure, and pulse;
- Score on the Glasgow Coma Scale;
- Score on the FAST;
- Time of stroke onset according to paramedics;
- Date and time of randomisation.

Baseline characteristics, assessed as part of usual clinical care at the time of hospital admission:

- Comorbidities/medical history: atrial fibrillation; diabetes mellitus; hypertension; pre-stroke mRS;
- Concurrent drugs: use of any blood-pressure-lowering drug in the 3 days before randomisation;
- Dates and times according to treating physician: stroke onset, hospital admission;
- Vital signs: blood pressure; pulse; body temperature;
- Neurological examination: NIHSS (see paragraph 8.3.4 and Appendix 4); (expected) location of the lesion (left or right hemisphere; posterior fossa);
- Laboratory examinations (see paragraph 8.3.6);
- Imaging results: stroke type: ischaemic stroke, intracerebral haemorrhage, or other relevant finding (see paragraph 8.3.7);
- Treatment restrictions (see paragraph 8.3.9);
- Stroke treatment: IVT with alteplase; IAT.

First 7 days or until discharge, if earlier:

- Vital signs: blood pressure and pulse at hourly intervals in the first 6 hours, at 2-hourly intervals between 6 and 24 hours, and daily thereafter;

- Final diagnosis (ischaemic stroke; intracerebral haemorrhage; other diagnosis);
- Cause of ischaemic stroke according to TOAST criteria;
- Treatment restrictions.
- Stroke treatment: early blood pressure reduction as acute treatment of intracerebral haemorrhage; surgery for intracerebral haemorrhage or decompressive hemicraniectomy for ischaemic stroke.

Safety parameters in first 7 days or until discharge, if earlier:

- Any serious adverse event (see paragraph 9.2.2);
- Hypotension requiring clinical intervention;
- Hypertension requiring clinical intervention;
- ‘Symptomatic intracerebral haemorrhage (sICH) scored according to the Heidelberg Bleeding Classification, with the addition of sICH that led to death and that was identified as the predominant cause of the neurologic deterioration.

Prehospital data that will be recorded:

Time of symptom onset/last seen well, time of call for help, time of 112 call, referrer of stroke, suspected diagnose (referrer), urgency code ambulance (A1/A2/B), time of arrival ambulance on site, time of departure ambulance towards hospital, name and postal code ambulance destination, time of arrival ER. When transfer from a primary stroke centre to an intervention centre takes place, we will also collect departure time of the primary stroke centre and arrival time at the ER of the intervention centre.

## 8.2 Randomisation, blinding and treatment allocation

Patients will be randomly allocated to open-label GTN 5 mg/day for one day, started within 3 hours of symptom onset, or to usual care. Randomisation will be through a web-based allocation service which will also allocate a unique study number to each patient.

Patients, paramedics, and treating nurses and physicians will be aware of the treatment allocation but the assessors of outcome at 90 days will remain blinded until the database has been locked. Information on treatment allocation will be kept separate from the main study database. The independent trial statistician will combine data on treatment allocation with the clinical data in order to report to the data safety monitoring board (DSMB). The treatment allocation code will not be broken until the database will have been locked, after the last patient has completed the final follow-up and all data have been cleaned.

### 8.3 Study procedures

#### 8.3.1 Baseline characteristics

See item 8.1.3. Baseline characteristics assessed by the paramedic will be included in the pre-hospital eCRF via a mobile device that is connected to the internet. The system will then also allocate a unique patient number.

#### 8.3.2 Vital signs

Blood pressure and pulse will be assessed at baseline in the prehospital setting and at hospital admission. Where assessed as part of routine clinical practice during hospital admission, blood pressure and pulse will be collected at hourly intervals ( $\pm 30$  minutes) in the first 6 hours, at 2-hourly ( $\pm 30$  minutes) intervals between 6 and 24 hours, and at 24-hour ( $\pm 4$  hours) intervals thereafter. Body temperature will be collected at hospital admission and at 24 ( $\pm 4$ ) hours. Both rectal and tympanic thermometry are allowed, but the method of thermometry will be noted in the eCRF. The assessment of vital signs will be discontinued at hospital discharge.

#### 8.3.3 Face-Arm-Speech Test (FAST)

FAST is used as a mnemonic to increase knowledge of stroke symptoms in the general population and to support diagnosis of stroke by paramedics. The FAST has been used in clinical practice for many years by the Dutch ambulance organisations. In a UK study, paramedics using the FAST achieved high levels of detection and diagnostic accuracy of stroke. In the present study, the score on the FAST will be assessed in the prehospital setting by the paramedic as part of routine clinical care, before inclusion in the study.

#### 8.3.4 National Institutes of Health Stroke Scale (NIHSS)

The NIHSS is an ordinal hierarchical scale to evaluate the severity of stroke by assessing a patient's performance (Appendix 4). Scores range from 0 to 42, with higher scores indicating a more severe deficit. The score on the NIHSS will be assessed at hospital admission and at 24 ( $\pm 4$ ) hours after study inclusion.

#### 8.3.5 Modified Rankin Scale (mRS)

The mRS is the preferred functional outcome measure in clinical stroke studies. The mRS is an ordinal hierarchical scale that describes the range of disabilities encountered post stroke, incorporating six categories from 0 (complete recovery) up to and including 5 (severe disability). 'Death' is assigned a score of 6 (Appendix 5). The mRS will be assessed at 7 ( $\pm 1$ ) days or at hospital discharge, if earlier, by a member of local study team, and at 90 ( $\pm 14$ )

days. Assessment of outcome on the mRS at 90 days will be performed by independent assessors, blinded to the allocated and actually received treatment. Their assessment will be based on standardised reports of a telephone interview by trained research personnel who are not aware of treatment allocation. Telephone assessment of the mRS with a structured interview has a good agreement with face-to-face assessment and can thus be used reliably in the setting of a clinical trial.

### **8.3.6 Laboratory tests**

If assessed at baseline as part of routine clinical practice, results from the following laboratory tests will be collected: INR; serum glucose; estimated glomerular filtration rate; C-reactive protein (CRP).

### **8.3.7 Imaging: lesion type and size; collateral circulation**

Brain CT or MRI will be performed as part of routine clinical care in each patient with suspected stroke. Results (e.g., visible ischaemic damage; intracerebral haemorrhage) will be noted in the eCRF. It is foreseeable that the majority of patients will also have CT angiography and perfusion of the brain, and a substantial minority DSA as part of routine clinical care in the context of IAT. No additional imaging will be performed as part of the present study. All imaging performed in the first week will be sent in a coded fashion to a central image institute for central evaluation of (where appropriate) perfusion deficits, arterial occlusion, early ischaemic damage, early lesion size, collateral circulation, and final lesion size. These evaluations will be performed blinded to treatment allocation. Algorithms for the assessment of these parameters will be developed during the course of the study.

### **8.3.8 Medication**

The times of the start and termination of study medication will be recorded. During the first 3 days (or up to discharge, if earlier), the use of any other antihypertensive drug will be recorded.

### **8.3.9 Treatment restrictions**

The presence of any treatment restriction will be recorded at baseline and during the first 7 days of hospital admission, and will be classified as 1. Do not resuscitate; 2. Do not intubate and ventilate; 3. Withholding other treatments that may prolong life; 4. Withholding food; 5. Withholding fluids; and 6. Palliation with morphine or a benzodiazepine. Any combination of these strategies is possible.

### **8.3.10 Barthel Index (BI)**

The BI is an ordinal scale used to measure performance in 10 activities of daily living (ADL). Test scores range from 0 to 100, with higher scores indicating better performance in these activities (Appendix 6). The BI will be assessed during the telephone interview at 90 days ( $\pm$  14 days).

### **8.3.11 EuroQoL (EQ-5D-5L)**

The EuroQoL 5-dimensions 5-level (EQ-5D-5L) questionnaire is a standardised measure of health outcome that has been used extensively in patients with stroke (Appendix 7). It is easy to understand and takes a few minutes to complete. The questionnaire is primarily designed for self-completion by patients, but if the patient is impaired in writing, the EQ-5D-5L may be completed by a representative of the patient or by the trial nurse, both as instructed by the patient. If the patient will not be able to complete the questionnaire because of aphasia or cognitive impairment, the patient's representative will do this instead of the patient. The EQ-5D-5L will be assessed during the telephone interview at 90 days ( $\pm$  14 days).

### **8.3.12 Patient location**

The location of the patient at noon of the relevant day during the Hospital Phase and follow-up phase will be recorded and classified as: hospital; rehabilitation service; chronic nursing facility; home (own or relative's). 'Home time,' defined as the number of nights among the first 90 since stroke onset that are spent in the patient's own home or a relative's home is a secondary outcome, for which the resource use will be censored at 90 days. Where final follow-up occurs earlier, the last known placement will be extrapolated to 90 days.

## **8.4 Withdrawal of individual subjects**

Subjects can leave the study at any time for any reason if they wish to do so without any consequences. The investigator can decide to withdraw a subject from the study for urgent medical reasons. The reason for withdrawal, if available, will be recorded in the eCRF. Data from non-consenting subjects will only be used when there is no written objection from the subject or representative. In an effort to describe the non-consenting population we will ask the subject or his/her representative to allow the use of routinely collected data in a coded manner. If no consent for the use of these data is obtained, only the following will be noted: study number, treatment allocation and refusal.

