### **8.5 Replacement of individual subjects after withdrawal**

For each patient that withdraws before the final outcome assessment, an additional patient will be included.

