### **8.6 Follow-up of subjects withdrawn from treatment**

In patients who discontinue their allocated treatment, this event will be recorded, including the reason for discontinuation if available. Further treatment will be at the discretion of the treating physician. Follow-up will be carried out as planned.

Due to the deferred consent procedure, study medication has been administered to patients randomised to GTN before informed consent has been obtained. Therefore it is not ethical, for the safety of all patients in the study, to eliminate all information of patients who do not provide informed consent in case of a serious adverse event in the first 7 days, or death during the full study period (both important safety variables for the study). Eliminating these records could result in an underestimation of the true risk of the study treatment and reduce the validity of the data and could lead to major safety concerns for all patients in case patients with a poor outcome will selectively withdraw from study participation. To overcome this safety concern, we will register for non-consenting patients only the variables: patient's study number, date of randomisation, study treatment, final diagnosis, investigator reported serious adverse events in the first 7 days (or until hospital discharge, if earlier), in-hospital mortality (yes/no). All other information will completely be erased from the patient's study record. The link to the study database will be erased from the medical record.

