## 10. STATISTICAL ANALYSIS

### 10.1 Statistical analysis plan (SAP)

The analysis and reporting of the trial will be in accordance with CONSORT guidelines. Before follow-up will have been completed, a statistical analysis plan (SAP) will be developed that will specify: (i) Hypotheses to be tested; (ii) Treatment effects to be estimated in order to satisfy the primary and secondary objectives of this trial; (iii) Technical description of the statistical methodology and procedures for performing the statistical analysis of outcome measures and SAE data; (iv) Primary, secondary, and sensitivity analyses; and (v) Subgroup analyses. The SAP will be signed off by the trial Executive Committee and then uploaded on the public area of the trial website. The final statistical analysis will be performed once recruitment has ceased, final follow-up has been completed, final data have been checked and any errors corrected, and the database has been locked.

All analyses will be performed according to the intention-to-treat principle. Baseline data by treatment allocation will be reported with statistical procedures. Missing values for baseline characteristics will be reported. Missing baseline characteristics will be imputed using regression imputation.

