#### e. Analysis of potential effect

In an individual-patient meta-analysis of four phase II stroke trials and one phase III trial of GTN in a total of 4197 patients with ischaemic stroke or intracerebral haemorrhage, GTN was associated with increased rates of headache (369/2033, 18.2%

versus 171/2026, 8.4%) and clinical hypotension (i.e., hypotension requiring medical intervention, 55/2033, 2.7% versus 15/2026, 0.7%). There were no differences in the rates of death, neurological deterioration, recurrent stroke, clinical hypertension, or serious adverse events by the end of the 7 to 12 days of randomised treatment. GTN did not have an overall benefit on functional outcome at 90 days. The effects of GTN on functional outcome were consistent among relevant subgroups of patients, except for sex and time to randomisation (Figure 2).

**Figure 2:** Effect of GTN versus no GTN on functional outcome at 90 days in subgroups of patients. Figure from Bath *et al.* 2016.

More details can be obtained from the large phase III Efficacy of Nitric Oxide in Stroke (ENOS) trial, which randomised 4011 stroke patients with raised systolic blood pressure (140–220 mm Hg) to 7 days of transdermal GTN (5 mg per day), started within 48 h of stroke onset, or to no GTN. Use of GTN lowered blood pressure (difference on day 1, –7.0/3.5 mm Hg;  $P < 0.0001$ ) but did not lead to an overall improvement in functional outcome at 90 days. There was no increase in serious adverse events with GTN (Table 1). The drug was also safe in patients with carotid occlusion or more severe stroke. Serious adverse events occurred in 271 (14%) patients randomised to GTN and in 261 (13%) patients randomised to control (OR, 1.05; 95% CI, 0.88 to 1.26).

[figure not shown]
In the prespecified subgroup of 273 patients who were randomized within 6 hours of symptom onset, the first dose of GTN lowered blood pressure by 9.4/3.3 mm Hg ( $P < 0.01$ ,  $P = 0.064$ ). Importantly, GTN improved functional outcome on day 90 (adjusted common odds

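### Section 8.4 lets the investigator withdraw a patient from the study, not only from the patch, for urgent medical reasons, and no passage secures that patient's 90-day mRS or vital status

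*Protocol*

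**What the plan says.** Section 8.4 names two ways out of the trial. Patients may leave when they wish, and separately: "The investigator can decide to withdraw a subject from the study for urgent medical reasons". The reason is recorded if available. What is collected after a withdrawal by the investigator is not stated.

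Section 8.6, headed as concerning withdrawal from treatment, opens: "In patients who discontinue their allocated treatment, this event will be recorded". For that group it adds: "Follow-up will be carried out as planned". The same section lists data kept for patients who do not consent: study number, randomisation date, treatment, final diagnosis, serious adverse events in the first 7 days or until discharge, and in-hospital death. That list has no 90-day mRS and no vital status at 90 days.

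Section 8.5 says: "For each patient that withdraws before the final outcome assessment, an additional patient will be included".

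On knowledge of allocation, section 8.2 says: "Patients, paramedics, and treating nurses and physicians will be aware of the treatment allocation". Only the assessors of the 90-day outcome are blinded.

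On analysis, section 10.1 says: "All analyses will be performed according to the intention-to-treat principle".

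**The concern.** The protocol separates stopping the treatment from leaving the study, but guarantees follow-up only after the first. A patient taken out of the study by the investigator falls between the rules. Section 8.6 does not reach such a patient, and section 8.5 appears to treat withdrawal as loss of the final outcome, to be made good by recruiting someone else.

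Three features make this more than a gap in wording. The trigger, an urgent medical reason, is related to prognosis. The person deciding may know the arm. The outcome at risk is the primary one. A replacement restores the number of patients but not the comparability of the randomised groups, and intention to treat cannot be applied to outcomes that were never collected.

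The protocol recognises this mechanism in section 8.6, in its discussion of patients who do not consent: "Eliminating these records could result in an underestimation of the true risk of the study treatment". The remedy there is confined to non-consenting patients.

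**Working it through.** **Step 1: is the power needed to stop treatment?** Section 5.3 includes patch removal in its stepped approach to symptomatic falls in blood pressure, and requires removal when an exclusion criterion comes to light within 24 hours. Section 6.6 allows removal before 24 ± 2 hours if clinically indicated. Stopping the patch therefore does not require leaving the study. What remains of participation is light: the Summary says that no imaging or laboratory test is added, and sections 8.3.5, 8.3.10 and 8.3.11 collect the 90-day scales by telephone interview. In the standard-care arm there is no study treatment to stop, so there the power can only end observation.

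**Step 2: is the 90-day outcome kept by any other rule?**

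| Patient | 90-day mRS secured? | Source |
|---|---|---|
| Stops the patch, stays in the study | Yes | 8.6 |
| Does not consent | No; short safety list only | 8.6 |
| Withdrawn from the study by the investigator | Not stated | 8.4; 8.5 implies loss |

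**Step 3: size.** The protocol states no withdrawal figure to reproduce. Its target of 1400 is 1280 × 1.10 = 1408, rounded; the 10% is for stroke mimics, not for withdrawal.

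Inputs: poor outcome (mRS 3–6) p = 48% and target reduction 7 points, both from section 4.4. A 1:1 allocation, giving 700 per arm, is assumed because the ratio is not stated. No true effect is assumed. A fraction f of one arm is lost, all of whom would have had a poor outcome. Replacements are not modelled.

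- Patients with poor outcome per arm: 0.48 × 700 = 336; others: 364.
- Observed risk in the arm with loss: (336 − 700f)/(700 − 700f).
- Shift: f(1 − p)/(1 − f). At f = 1%: 0.01 × 0.52/0.99 = 0.53 points.
- Odds ratio for poor outcome, arm with loss against the other: (336 − 700f)/336.
- Two-sided rejection rate at nominal 5%: normal approximation to the log odds ratio, with the standard error from the four cell counts. At f = 3%: ln(315/336) = −0.0645; SE = √(1/336 + 1/364 + 1/315 + 1/364) = 0.108; z = −0.60; rejection 9.2%.

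| Lost from one arm | Patients | Observed risk | Shift (points) | Odds ratio | Rejection rate |
|---|---|---|---|---|---|
| 1% | 7 | 329/693 = 47.5% | 0.5 | 0.98 | 5.4% |
| 2% | 14 | 322/686 = 46.9% | 1.1 | 0.96 | 6.8% |
| 3% | 21 | 315/679 = 46.4% | 1.6 | 0.94 | 9.2% |
| 5% | 35 | 301/665 = 45.3% | 2.7 | 0.90 | 17.3% |

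**Step 4: sensitivity.**
- If only 75% of those lost would have had a poor outcome, the shift is f(0.75 − 0.48)/(1 − f), about 0.3 points per 1%.
- If all those lost would have had mRS 5–6, a rank test gives rejection rates of about 6%, 9%, 14% and 26% at 1%, 2%, 3% and 5% loss. This comes from 1,500 simulated trials per setting, with an assumed mRS 0–6 distribution of 12, 20, 20, 14, 14, 5 and 15%.
- If 2% of each arm is lost, all with poor outcome, both arms read 46.9% and there is no shift.

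**The case against.** A reader might infer that the lost patients would come mostly from the GTN arm, so that the bias favours GTN. There is some ground for this: only that arm has a study treatment to stop, and section 13.1(e) reports hypotension needing intervention in 55/2033 (2.7%) against 15/2026 (0.7%) in earlier trials. But the same section gives serious adverse events of 14% and 13% in the large phase III trial of GTN. Bad early courses occur in both arms, and no split of withdrawals is given. More frequent loss under GTN is possible but not established.

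A reader might also apply the hypotension rates to 700 per arm. If every such patient left the study and would have had a poor outcome, the risks would be (0.48 − 0.027)/(1 − 0.027) = 46.6% and (0.48 − 0.007)/(1 − 0.007) = 47.6%, a spurious 1.1 points. That is not a forecast. Section 5.3 manages symptomatic hypotension in steps up to patch removal, after which section 8.6 keeps follow-up. The rates also come from trials with 7 to 12 days of treatment, against 24 hours here.

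It would go too far to say that the rule hides a harm signal. Serious adverse events to day 7 are reported or documented and followed (9.2.2, 9.4). Hypotension needing intervention and symptomatic haemorrhage are separate safety parameters (8.1.3), and the DSMB sees unblinded summaries (9.5). What is exposed is the later mRS and later death.

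Nor does section 8.4 contradict intention to treat. It does not say that withdrawn patients are dropped from analysis, and whether section 8.5 reaches withdrawal by the investigator is itself unclear. Handling of missing outcomes may be set out in a statistical analysis plan that is not shown. That does not remove the point: an analysis plan cannot recover an outcome that the protocol allowed not to be collected.

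**Conclusion.** The point stands as a poorly drawn rule. As written, section 8.4 permits a prognosis-related exit from the study, decided by someone who may know the arm, with no passage securing the 90-day mRS or vital status. This undermines the intention-to-treat analysis, and replacement under section 8.5 does not repair it.

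The size can be given only as a range, because the protocol states neither a rate nor a split by arm. The effect is small at 1–2% one-sided loss and becomes material at 3–5%. The direction depends on which arm loses more patients. These figures rest on no true effect, 48% poor outcome, 700 per arm and, in the main table, poor outcome in every patient lost.

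**What to change.** Reconcile sections 8.4, 8.5, 8.6 and 10.1:

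- In 8.4, have withdrawal by the investigator end study treatment only, with follow-up continuing under 8.6.
- State that 90-day mRS and vital status are still collected, and analysed in the randomised arm, unless the patient or representative withdraws consent.
- In 8.5, make clear that such patients are not replaced, since they remain in the trial.
- Report the number of such cases and their reasons by arm.

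Which medical reasons justify stopping the patch is left to the clinicians. The cost is a few sentences in the next amendment. No visits are added, because section 8.6 already requires this follow-up for patients who stop treatment.
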